## 3 Study Design

### 3.1 General Design

In this pilot randomized double blind placebo controlled study we wish to assess the ability of oral  $\omega$ 3 free fatty acids to downregulate pro-neoplastic and pro-inflammatory pathways in the esophagus. Pilot data from this proposal will enable us to design a larger adequately powered study assessing the role of  $\omega$ 3 free fatty acids as chemoprevention agents in subjects with BE, who are at substantial risk of developing EAC, a lethal cancer with rapidly rising incidence in the United States. Our plan is to complete the study on 80 participants, 40 in each group randomized to omega-3 or placebo. Subjects between 18-85 years of age, with known BE (no dysplasia and low-grade dysplasia) will be identified using an existing GI database for participation in this study. Invitation letters will be mailed to eligible subjects. Subjects meeting inclusion and exclusion criteria will be screened and consented. Once consent has been obtained baseline assessment and endoscopy with biopsy/brushings, and endoscopic mucosal impedance measurement will be completed. A single slice CT scan of the abdomen will also be obtained at baseline for each subject to quantify visceral and subcutaneous fat area in the abdomen. Subjects will then begin treatment and follow-up for the next 6 months. A final visit for evaluation and collection of tissue samples will be conducted at the end of the study. No risks of any particular seriousness or severity are anticipated. Blood and tissue samples will be obtained and used in this study as outlined in section 3.2. Any remaining samples will be stored in [name] -80C freezer located at Joseph M97 and used for future research in Barrett's esophagus.

Modulation of Esophageal Inflammation in Barrett's Esophagus by  $\omega$ 3 Fatty Acids

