### 3.2 Study Endpoints

The primary analysis objective in this pilot study is to estimate response magnitude and variation in esophageal inflammation and injury in BE as measured by tissue PGE2, the esophageal inflammation score, esophageal macrophage infiltration and modulation of esophageal macrophage phenotype attributable to  $\omega$ 3 FFA supplementation. This will be the information needed to design a larger adequately powered study to study the efficacy of  $\omega$ 3 FFA as a chemoprevention agent in BE.

**Aim 1:** The **primary response** outcome is tissue PGE2 levels and the main secondary response outcome is the histologic score of 3 or 4 (severe grades of inflammation). Other **secondary outcomes** include pre and post supplementation serum and tissue  $\omega$ 3 FFA levels.

**Aim 2:** The **primary response** outcome is the cytokine expression profile in esophageal biopsies as measured by qPCR [IL1 $\beta$ , IL6 (M1 markers) versus IL1, IL10 (M2 markers)]. **Secondary response outcomes** include change in esophageal macrophage counts and phenotype proportions (total, %M1, %M2).

**Aim 3:** The primary response outcome is change in esophageal mucosal impedance (baseline-post treatment) which is a physiologic correlate of the epithelial barrier function, with  $\omega$ 3 FFA supplementation. Secondary outcomes include the association of esophageal mucosal impedance with measures of central obesity (waist circumference, waist hip ratio and abdominal visceral fat area on CT) at baseline and following treatment.

**Aim 4:** The primary response outcome is the change in the esophageal microbiome in BE subjects following  $\omega$ 3 FFA supplementation. Secondary outcomes will be the association of the microbiome pattern with measures of central obesity ((waist circumference, waist hip ratio and abdominal visceral fat area on CT).

Assays performed at baseline and at 6 months will include:

*Aim 1:* Primary outcome: Tissue PGE2 in esophageal biopsies. This will be performed by previously described methods [21] on esophageal biopsies snap frozen at -80^0 C in [name] laboratory.

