## 7 Statistical Plan

### 7.1 Sample Size Determination

#### Statistical Analysis

Up to 90 patients with Barrett's will be identified and randomized to either drug or placebo. The primary analysis objective in this pilot study is to estimate response magnitude and variation which will be the information needed to design a larger adequately powered study to study the efficacy of  $\omega$ 3FFA as a chemoprevention agent in BE. The data will be summarized as mean, standard deviation, as well as median, and interquartile range, overall (baseline) and by treatment group (post-supplementation at 6 months). In addition, 95% confidence intervals for response mean (or median) treatment group values and 95% confidence intervals for treatment group differences in means (or medians) will also be calculated. Exploratory descriptive summaries of the response data will also be generated after stratifying on ASA intake.

Aim 1: The primary response outcome is tissue PGE2 levels and the main secondary response outcome is the histologic score of 3 or 4 (severe grades of inflammation). Other secondary outcomes include pre and post supplementation serum and tissue  $\omega$ 3 FFA levels.

Aim 2: The primary response outcome is the Cytokine expression profile in esophageal biopsies as measured by qPCR [IL1 $\beta$ , IL6 (M1 markers) versus IL1, IL10 (M2 markers)]. Secondary response outcomes include change in esophageal macrophage counts and phenotype proportions (total, %M1, %M2).

Aim 3: The esophageal mucosal impedance of the squamous epithelium and columnar epithelium will be summarized as mean (SD) or median (IQR) depending on data normality. The data will be summarized (baseline and post-supplementation) by treatment group. Change in impedance (Baseline – post supplementation) will be compared using appropriate statistical tests. Secondary outcome analysis will include testing the association between esophageal mucosal impedance and measures of central obesity (including waist circumference, waist hip ratio and abdominal visceral fat area on CT scan).

Aim 4:

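### Aim 3 compares change in mucosal impedance with no named test and no baseline adjustment; pre-specifying a baseline-adjusted model is a free gain in precision

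*Combined protocol and SAP*

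**What the plan says.** Section 3.2 (Study Endpoints) defines the Aim 3 endpoint: "The primary response outcome is change in esophageal mucosal impedance (baseline-post treatment"). The Statistical Analysis text in section 7.1 gives the comparison: "Change in impedance (Baseline – post supplementation) will be compared using appropriate statistical tests". The descriptive output for the same aim is: "The data will be summarized (baseline and post-supplementation) by treatment group", as mean (SD) or median (IQR).

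The general paragraph of section 7.1 sets the purpose: "The primary analysis objective in this pilot study is to estimate response magnitude and variation". The between-arm estimate it promises is: "95% confidence intervals for treatment group differences in means (or medians) will also be calculated". No regression model or covariate is named for Aims 1 to 3.

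The Schedule of Events places the impedance measurement at month 0 and month 6, so the baseline value is already collected. On size, section 3.1 says "Our plan is to complete the study on 80 participants, 40 in each group randomized to omega-3 or placebo", while section 7.1 says "Up to 90 patients with Barrett's will be identified and randomized to either drug or placebo". The documents give no SD, pre-post correlation, target difference or power for impedance.

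**The concern.** A simple change score subtracts the whole baseline reading, which fixes the baseline slope at 1. When the pre-post correlation is below 1, and the variances at the two visits are similar, the best-fitting slope is smaller than 1. The change score then over-corrects and carries baseline noise into the outcome. A linear model that estimates the slope targets the same arm difference with a smaller residual variance.

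What is at stake is precision. This is an estimation pilot, so the main product for Aim 3 is an estimated arm difference and its confidence interval. Leaving out the baseline covariate makes that interval wider than the collected data require. Leaving the test unnamed also means that the choice could be made after the data are seen.

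**Working it through.** There is no planned figure to reproduce, because the plan states no precision or power for impedance. The check therefore compares the two analyses under stated assumptions.

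**Inputs**
- 40 per arm completing (section 3.1).
- 95% confidence intervals (section 7.1).
- Assumed: equal variance s² at baseline (X) and month 6 (Y), the same in both arms.
- Assumed: pre-post correlation ρ of 0.3, 0.5, 0.7 or 0.8.

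**Formulas**
- Unadjusted change: Var(X − Y) = s² + s² − 2ρs² = 2(1 − ρ)s².
- Month 6 adjusted for baseline: residual variance = (1 − ρ²)s².
- Variance ratio, adjusted to change: (1 − ρ²) / [2(1 − ρ)] = (1 + ρ)/2.
- Interval-width ratio: √[(1 + ρ)/2].

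| Assumed ρ | SD of change (in s) | Adjusted residual SD (in s) | Variance ratio | Width ratio | Interval narrower by |
|---|---|---|---|---|---|
| 0.3 | 1.183 | 0.954 | 0.65 | 0.806 | 19% |
| 0.5 | 1.000 | 0.866 | 0.75 | 0.866 | 13% |
| 0.7 | 0.775 | 0.714 | 0.85 | 0.922 | 8% |
| 0.8 | 0.632 | 0.600 | 0.90 | 0.949 | 5% |

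**Half-widths at ρ = 0.5, 40 per arm**
- Change: t(78 df) × 1.000 × √(2/40) = 1.991 × 0.2236 = 0.445 s.
- Adjusted: t(77 df) × 0.866 × √(2/40) = 1.991 × 0.1936 = 0.386 s.
- Ratio: 0.386/0.445 = 0.87, which agrees with the table. The lost degree of freedom has almost no effect.

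The width ratio does not depend on the number of subjects, so the difference between 80 completing and up to 90 randomized does not affect the percentages.

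**If the promised intervals refer to month-6 values instead.** The general paragraph can be read as comparing post-supplementation values. Adjustment helps there too: the variance ratio of adjusted to month-6-only is 1 − ρ², which is 1 − 0.25 = 0.75 at ρ = 0.5. The direction of the finding is the same under either reading.

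**The case against.** The strongest objection is that the plan does not say the comparison is unadjusted. It leaves the test open, and the sentence does not itself mention arms. A linear model of change with baseline as a covariate would fit the wording. Apart from sign, it gives the same arm estimate, standard error and p-value as the same model for the month-6 value. This stands: choosing change as the outcome is not a defect, and a reader who infers that the plan has committed to raw change scores goes further than the text. What remains is that adjustment is not specified, and that the only between-arm estimates promised are plain differences in means or medians.

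Four stronger readings are tempting, and the documents do not support them.

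- **A loss of about 10 percentage points of power.** This needs both ρ = 0.5 and 80% power for the change-score analysis (80% rising to 89.9%), and the plan states neither. At ρ = 0.5 and 40 per arm, the gain is 3.4 points for a true difference of 0.2 SD, 12.4 points for 0.5 SD and 3.8 points for 0.8 SD. Interval width is the right measure for an estimation pilot.
- **A next trial one third too large (1/0.75).** Section 3.2 names the responses needed to design the larger study as PGE2, the inflammation score, macrophage infiltration and macrophage phenotype. Impedance is not among them. The paired readings would in any case let designers compute the correlation.
- **Bias from chance baseline imbalance as a further harm.** Under randomization the change-score contrast is unbiased. Chance imbalance is part of the variance loss already counted in (1 + ρ)/2.
- **The same fault in Aim 2.** For macrophages the plan says "Secondary response outcomes include change in esophageal macrophage counts and phenotype proportions", but it states no method of comparison for those changes, so there is no change-score analysis to criticise.

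**Conclusion.** The point holds as a free improvement. Aim 3 names no test and specifies no baseline adjustment, and the literal reading is an unadjusted comparison of change. Under equal variances, baseline adjustment narrows the interval for the arm difference by about 19% to 5% as the assumed correlation goes from 0.3 to 0.8.

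The direction needs only equal variances and a correlation below 1, apart from the small cost of estimating one slope. The size rests wholly on the correlation, which the documents do not give. If readings were averaged over the several sites listed in section 3.2, the correlation could be higher and the gain smaller. Nothing here makes the planned comparison invalid.

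**What to change.** Replace the Aim 3 comparison sentence in section 7.1 with:

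> Month-6 impedance (or change) will be compared between arms by a linear model with arm and baseline impedance at the same site as covariates (log or rank scale if skewed). The adjusted difference, 95% CI, residual SD and pre-post correlation will be reported.

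Reporting the residual SD and the correlation also serves the pilot's aim of describing variation, because separate baseline and post-supplementation summaries do not show how the two readings move together.

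The cost is one sentence and one degree of freedom. No new measurement, visit or subject is needed.

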Secondary outcomes: 1. Tissue inflammation score (grade 0-3). This will be performed on esophageal H&E stained sections as previously described [5], by [name], an experienced gastrointestinal pathologist. 2. Esophageal tissue EPA levels: this will be performed on esophageal biopsies obtained at baseline and at 6 months, in the Metabolomics Core laboratory. 3. Serum  $\omega$ 3 FFA levels: will be performed using mass spectroscopy/liquid chromatography in the Immunochemistry Core laboratory at baseline and 6 months.

*Aim 2:* Primary outcome: 1. Quantification of esophageal macrophage infiltration (and subtypes) by qPCR for CD68 (macrophage marker) TNF $\alpha$  and MCP1 (M1 markers) and CD206, IL1, IL10, as M2 markers). This will be performed in collaboration with [name] (see preliminary data and letter of support) using previously described standard methodology [29].

Secondary outcomes : Esophageal macrophage counts (using CD68 and HAM 56 as markers) and proportion of M1 and M2 (CD206) using immunofluorescence will be performed using previously described methods [24]. Cells double labeled for CD206 and CD68 will be categorized as M2 cells and those staining only with CD68 will be categorized as M1 cells. Cell counts will be performed as previously described.

Aim 3: Esophageal mucosal impedance measurements will be obtained using a esophageal mucosal impedance catheter at 2 cm, 5 cm and 7 cm above the GEJ. At least one measurement will be obtained in the squamous mucosa at 3 cm above the BE segment [30].

Aim 4: The esophageal microbiome will be characterized from biopsies and brushings from the squamous and columnar epithelium using standard methods.

Sequencing : Biopsy samples and brushings will be collected in cryo-vials and flash frozen in liquid nitrogen. All samples will be stored at -80 till they are ready for processing.

Next Generation sequencing:

Bacterial DNA will be enriched in biopsy and brushings using NEBNext microbiome DNA enrichment kit if concentrations are low. Amplicons spanning the variable region 4 (V4) of bacterial 16SrRNA will be generated using a barcoded reverse primer (515F, 806R). Samples will be sequenced using the MiSeq platform at Mayo Genome Facility to obtain 300bp paired end reads. Based on our previous experience we will sequence at most 100 samples in one sequencing run and we expect ~30,000 high quality reads per sample.

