#### 4.3 **Subject Recruitment, Enrollment and Screening**

Subjects between 18-85 years of age, with known BE (no dysplasia and low-grade dysplasia) will be identified using an existing GI database for participation in this study. Invitation letters will be mailed to eligible subjects. Subjects will be called to discuss study and scheduled for a screening visit. Subjects taking  $\omega$ 3 FFA as a supplement will discontinue use at least four weeks prior to visit 1. Subjects will report fasting 12 hours for this visit. Subjects meeting inclusion and exclusion criteria will be screened and consented. Baseline assessment will include the measurement of height, weight, waist circumference, hip circumference and waist/hip ratio using standard methods of anthropometric measurements. A comprehensive medication list will be obtained. Patients will also fill out the Reflux Symptom Questionnaire (RSQ)/GER Questionnaire a validated instrument to assess reflux symptoms All patients will continue their baseline PPI regimen to control gastroesophageal reflux. 20cc of blood will be drawn after 12 hours of fasting to obtain a baseline serum FFA profile . Clinical baseline blood will be drawn for inclusion/exclusion: INR, LDL, AST and ALT. Endoscopy will then be performed in a standard manner. Six biopsies will be obtained from the GE junction, and seven biopsies from the BE mucosa 1 cm above the GE junction. Two biopsies from each site will be formalin fixed and paraffin embedded (for inflammatory score assessment) and the remainder frozen at  $-80$  C for subsequent analysis. An additional seven biopsies will be obtained from the squamous mucosa at least 3 cm above the proximal end of the BE segment. Two will be placed in formalin (or other fixative) and paraffin embedded (IHC for macrophage cell counts) and the remainder will be snap frozen at  $-80^{\circ}$  C (PGE2 levels). Endoscopic brushings of the Barrett's segment as well as squamous tissue will be obtained and frozen for each subject. Endoscopic mucosal impedance measurement will be completed during endoscopy. A single slice CT scan of the

abdomen will also be obtained at baseline for each subject to quantify visceral and subcutaneous fat area in the abdomen.

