**6.2 Visit 2**

Subjects will undergo repeat assessment at six months following randomization. This will include anthropometry (similar to baseline), a fasting blood draw and endoscopy with research biopsies and brushings as outlined at baseline. Subjects will also fill out the Reflux Symptom Questionnaire (RSQ)/GER Questionnaire. Remaining medication will be counted and recorded.

If the participant is to be scheduled for a clinically indicated upper endoscopy and procedures that are ordered cannot be done on the Clinical Research Unit, (i.e. radiofrequency ablation, endoscopic mucosal resection, esophageal dilation, endoscopic ultrasound) the research portion of the procedure will be done during the clinically indicated upper endoscopy. These research procedures will include biopsies and brushings of the esophagus as well as mucosal impedance.

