We will align the paired end reads using PANDASeq given our small amplicon size (~392bp) which allows for significant overlap in the two reads. Data will be processed using QIIME1.8.0 (Quantitative Insights Into Microbial Ecology) analysis pipeline. OTUs (Operational Taxonomic Units) will be determined at 97% sequence similarity using uclust, taxonomy will be assigned using RDP classifier against the GreenGenes database, and a phylogenetic tree will be built using FastTree. The OTU table will be rarified at a single sequencing depth. We will compare alpha diversity using both phylogenetic (PD whole tree) and non-phylogenetic measures (Shannon, observed species and Chao1) to assess evenness and richness of distribution. We will compare beta diversity using both phylogenetic (UniFrac) and count based metrics (Bray-Curtis).

Statistical analysis of differences between groups and changes within the microbiome will be performed such as using PERMANOVA to compare beta diversity. Differences in individual taxa between groups will be assessed using ANOVA with correction for multiple hypotheses testing using FDR. A p-value of <0.05 will be considered statistically significant. Additional

analysis to impute potential changes in gene content (PICRUSt) and pathways (HUMANN) will be done depending on the results of initial analysis.

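### Aim 4's primary outcome is a change measured on up to eight sample classes per subject, but its tests are named without a baseline term, subject term, pairing or permutation unit

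*Combined protocol and SAP*

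**What the plan says.** Section 3.2 defines the Aim 4 primary outcome as a change: "The primary response outcome is the change in the esophageal microbiome in BE subjects following" ω3 FFA supplementation. The same section sets out the material: "The esophageal microbiome will be characterized from biopsies and brushings from the squamous and columnar epithelium using standard methods". Section 4.3 confirms brushings at both sites ("Endoscopic brushings of the Barrett's segment as well as squamous tissue will be obtained and frozen for each subject"), and Section 6.2 repeats the collection at six months ("a fasting blood draw and endoscopy with research biopsies and brushings as outlined at baseline").

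The analysis of these samples is in the Aim 4 part of the Statistical Analysis text in Section 7.1. It says that differences between groups and changes within the microbiome will be analysed, and it gives PERMANOVA on beta diversity as an example. For taxa it states "Differences in individual taxa between groups will be assessed using ANOVA with correction for multiple hypotheses testing using FDR". The significance threshold is p<0.05.

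The text does not define the groups (arm, visit, site or sample type). It names no unit of analysis, baseline covariate, subject effect or restriction on permutations, and it does not say whether sites and sample types are analysed together or apart. Aim 3, in the same section, does define a change (baseline minus post-supplementation) and says that it will be compared. Aim 4 has no equivalent.

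**The concern.** Samples from one person resemble each other. Two kinds of error are possible, and the text leaves both open.

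- **Between arms.** If several samples per subject enter an ANOVA or a freely permuted PERMANOVA as independent observations, the effective sample size is overstated and p-values are too small. FDR control does not help, because it takes the p-values as valid.
- **Change over time.** If baseline is left out, or the two visits are compared as unpaired groups, the information in the paired design is lost and standard errors are larger than they need be.

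The stated purpose of the pilot is to estimate the size and variation of response so that a larger trial can be designed, and confidence intervals suffer in the same way as tests. Section 7.1 also makes the follow-on gene-content and pathway analyses depend on the initial results, so a spurious finding could be carried forward.

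**Working it through.** The documents give no power, effect size, standard deviation or correlation for Aim 4, so there is no planned figure to reproduce. The correlations below are assumptions, shown over a range.

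**Inputs**
- Sample classes per subject: 2 sample types × 2 epithelia × 2 visits = 8, or 4 per visit (Sections 3.2, 4.3, 6.2). This assumes one sequenced sample per class. Several biopsies are taken at each site, and GE junction biopsies are taken as well.
- Subjects: 80, 40 per arm (Section 3.1), or up to 90 (Section 7.1).
- α = 0.05 (Section 7.1); two-sided is assumed.

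**1. Arm test with one visit's four samples pooled as independent.** Let r be the correlation between samples from the same subject, taken as equal across site and type. The variance inflation is 1 + (4 − 1)r, and the true error is 2[1 − Φ(1.96/√(1 + 3r))].

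| r | inflation | true error |
|---|---|---|
| 0.1 | 1.3 | 0.086 |
| 0.3 | 1.9 | 0.155 |
| 0.5 | 2.5 | 0.215 |
| 0.7 | 3.1 | 0.266 |

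Simulation of the two-group ANOVA at 40 per arm (4,000 replicates) gave 0.088, 0.155, 0.215 and 0.264. Using subject means as the unit brought it back to 0.050–0.055.

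PERMANOVA on Bray-Curtis distances (30 simulated taxa, 200 replicates, 199 permutations, four samples per subject) rejected in 0.18, 0.42 and 0.71 of null data sets at r = 0.1, 0.3 and 0.5 when samples were permuted freely. Permuting whole subjects gave 0.04, 0.05 and 0.04 (Monte Carlo SE about 0.015).

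With Benjamini-Hochberg FDR control over 100 independent null taxa and four pooled samples, the chance of at least one false discovery was 0.19, 0.73 and 0.95 at r = 0.1, 0.3 and 0.5. With one sample per subject it was 0.045.

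**2. Each site and sample type analysed separately, one sample per subject at month 6.** Simulated ANOVA error was 0.044–0.059, so there is no inflation. Efficiency is a different matter. Let ρ be the correlation between a subject's baseline and month-6 values in the same site and type. In units of the outcome variance, the month-6 comparison has variance 1 and the baseline-adjusted comparison 1 − ρ², so the standard error ratio is 1/√(1 − ρ²):
- ρ = 0.3: 1/√0.91 = 1.05
- ρ = 0.5: 1/√0.75 = 1.15
- ρ = 0.7: 1/√0.51 = 1.40

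At an assumed effect of 0.5 SD and 40 per arm, power is 0.61 for month 6 alone, and 0.65, 0.73 and 0.88 with baseline adjustment at these correlations.

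A raw change score has variance 2(1 − ρ), so it beats month 6 alone only when ρ exceeds 0.5. Its power is 0.47, 0.61 and 0.82. Baseline adjustment is therefore the better choice.

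**3. Within-arm pre-post test run as unpaired.** The standard error ratio to the paired test is √2/√(2(1 − ρ)) = 1/√(1 − ρ). At ρ = 0.5 this is 1.41, or 41% too large; at 0.3 it is 1.20 and at 0.7 it is 1.83.

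**4. Sequencing runs.** 80 × 8 = 640 and 90 × 8 = 720 samples. Section 3.2 says "we will sequence at most 100 samples in one sequencing run". 640/100 = 6.4 and 720/100 = 7.2, so at least 7 to 8 runs are needed.

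**The case against.** The plan is silent; it does not declare samples independent. Its Aim 4 text mentions change and offers PERMANOVA only as an example. Elsewhere Section 7.1 summarises results by arm at six months, and Aim 3 names squamous and columnar epithelium separately. A competent analyst could well run each stratum on its own, and the error would then be about 5%. All of this stands, and it rules out four stronger readings that a reader might infer.

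- **That the tests are anti-conservative as planned.** The inflation is conditional on pooling, which no passage describes. Pooling all eight classes would give an error of 13% to 42% over the same correlations. That would mean putting pre-treatment samples into an arm test, and nothing in the documents suggests it.
- **That a between-group ANOVA cannot estimate the effect.** Randomization balances baseline in expectation, so for taxon means and alpha diversity the month-6 arm difference has the same expectation as the arm difference in change. What is lost is precision.
- **That the 41% applies to the arm comparison.** It applies only to an unpaired pre-post test within an arm.
- **That sequencing order biases the result.** Samples are held at −80 until processing, so runs can be laid out freely. A shift between visits would affect both arms alike and largely cancel in the randomized contrast.

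It is also fair that this is an estimation pilot, and that the overall primary analysis objective in Section 3.2 lists PGE2, the inflammation score and macrophage measures, not the microbiome.

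The objection does not remove the gap. The plan does not commit to separate analyses, and separate analyses would still leave the paired baseline unused. Aim 4 also sets its own significance threshold.

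**Conclusion.** The point holds as an improvement that costs nothing in data. Aim 4 names a change as its primary outcome, and its named tests come with no baseline term, subject term, pairing or permutation unit.

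The consequence depends on what the analyst does. Pooling one visit's samples would raise the true error of a 5% arm test to between 9% and 27%. Analysing strata separately without baseline keeps the error near 5% but gives standard errors 5% to 40% larger than necessary for correlations of 0.3 to 0.7. These sizes rest on assumed correlations, on equal correlation across site and sample type in the pooled case, and on one sequenced sample per class. The finding is that the method is not specified and a better one is available, not that the plan has chosen a wrong one.

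**What to change.** In the Aim 4 analysis text, state that the subject is the unit of analysis, and specify:

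- **Taxa and alpha diversity.** For each site and sample type separately, compare arms on the month-6 value adjusted for the baseline value. A mixed model with a subject random effect and an arm-by-visit term is an alternative. Keep FDR control across taxa.
- **Beta diversity.** For arm effects, permute arm labels over whole subjects. For visit effects, restrict permutations to within subject. For the arm difference in change, permute arm labels over whole subjects on a per-subject change measure, for example the arm-by-visit term with each subject's two visits kept together.
- **Sequencing (a minor, separate point).** Place both visits of a subject in the same run and balance arms across runs.

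The cost is revised analysis wording, a run layout and slightly more analysis work. No further samples, visits or procedures are needed.

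### Aim 4 sets p<0.05 as its significance rule for six diversity metrics, names none as primary, and states a multiplicity correction only for individual taxa

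*Combined protocol and SAP*

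**What the plan says.** Section 3.2 defines the Aim 4 primary outcome in general terms: "The primary response outcome is the change in the esophageal microbiome in BE subjects following" omega-3 supplementation. It gives no metric, tissue site, specimen type or contrast. The same section describes the material: "The esophageal microbiome will be characterized from biopsies and brushings from the squamous and columnar epithelium using standard methods".

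The Aim 4 text in section 7.1 lists the analyses:

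- Alpha diversity: "We will compare alpha diversity using both phylogenetic (PD whole tree) and non-phylogenetic measures (Shannon, observed species and Chao1"), which is four metrics.
- Beta diversity: "We will compare beta diversity using both phylogenetic (UniFrac) and count based metrics (Bray-Curtis"), which is two metrics. Whether UniFrac is weighted, unweighted or both is not stated.
- Contrasts: "Statistical analysis of differences between groups and changes within the microbiome will be performed such as using PERMANOVA to compare beta diversity". Two kinds of comparison are mentioned, and PERMANOVA is given as an example.
- Taxa: "Differences in individual taxa between groups will be assessed using ANOVA with correction for multiple hypotheses testing using FDR".

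The significance rule follows directly: "A p-value of <0.05 will be considered statistically significant". No text ranks the diversity comparisons, corrects them, or calls them exploratory.

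**The concern.** A change in the microbiome is not a single variable. With six summaries of it, one threshold and no ranking, any metric that crosses 0.05 could be reported as the answer to the Aim 4 primary question. The plan accepts that multiplicity matters, because it corrects the taxon tests. The diversity tests, which bear most directly on the primary outcome as worded, have no stated correction.

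Two things are at stake. The first is the false-positive rate behind any statement that the microbiome changed. The second is the estimate itself: a metric selected because it crossed the threshold tends to overstate the effect. Section 7.1 also makes the follow-on gene-content and pathway analyses depend on the initial results, and it expects the trial's data to support a grant application. A chance result could therefore be carried further.

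**Working it through.** The documents give no count of Aim 4 tests and no familywise error rate, so there is no stated figure to reproduce.

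**Inputs from the documents**

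- Threshold: 0.05 per test (section 7.1). Sidedness is not stated; two-sided is assumed.
- Metrics: 4 alpha + 2 beta = 6 (section 7.1).
- Sample classes: 2 specimen types x 2 epithelia = 4 (section 3.2). Whether they are tested separately or pooled is not stated.

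**Inputs assumed**

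- Correlations between test statistics. The documents give none, so a range is shown: 0.6 to 0.9 between metrics within a sample class, and 0.2 to 0.8 between classes.

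**Step 1. Number of tests**

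- One contrast in one class: 6. This is the smallest count that the documents support.
- One contrast in each of four classes: 6 x 4 = 24. This holds only if the classes are analysed separately.

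**Step 2. No omega-3 effect, independent tests**

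Chance of at least one p<0.05 = 1 - 0.95^k. Expected number of false positives = 0.05 x k.

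| k | At least one p<0.05 | Expected false positives |
|---|---|---|
| 6 | 1 - 0.95^6 = 26.5% | 0.3 |
| 24 | 1 - 0.95^24 = 70.8% | 1.2 |

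**Step 3. No omega-3 effect, correlated tests**

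The metrics come from the same samples, so positive correlation is expected and independence gives the high end. Normal test statistics were simulated with a common correlation within a class and a lower one between classes (two-sided 5%, at least 200,000 draws per setting).

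| Tests | Within class | Between classes | At least one p<0.05 |
|---|---|---|---|
| 6 | 0.6 | - | 19% |
| 6 | 0.7 | - | 16% |
| 6 | 0.8 | - | 14% |
| 6 | 0.9 | - | 11% |
| 24 | 0.6 | 0.2 | 54% |
| 24 | 0.7 | 0.3 | 47% |
| 24 | 0.8 | 0.5 | 36% |
| 24 | 0.9 | 0.8 | 21% |

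**Step 4. After the change**

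One named primary test at 0.05 has a false-positive rate of 5%. Every setting above exceeds that, by a factor of about 2 (11/5) to 5 (26.5/5) for six tests.

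**The case against.** **The count.** A reader might infer that at least 24 tests are planned. The documents do not say so. The factor of four comes from a description of how specimens are obtained in section 3.2. Pooling the classes, or modelling site as a factor, is equally open. This objection stands: six is the documented floor and 24 is conditional.

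**Likelihood.** A reader might also infer that a false positive is likely. With 24 correlated tests the range is about 21-54%, and only the least correlated setting shown exceeds one half. With six tests it is 11-27%. Several of the alpha metrics measure richness from the same rarefied table, so high correlation is plausible. This also stands. The rates are inflated, but the documents do not support calling a false positive likely.

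**Consequence.** It is tempting to say that a chance microbiome finding would pass straight into the design of the next study. Section 3.2 lists what that study needs: tissue PGE2, the inflammation score, macrophage infiltration and macrophage phenotype. The microbiome is not on the list. Section 2 words Aim 4 descriptively, section 7.1 makes estimation the pilot's main objective with 95% confidence intervals for group values and differences, and no go/no-go decision rests on an Aim 4 p-value. This limits the weight of the point but does not remove it. Aim 4 still adopts a significance rule, and estimation also needs a named quantity.

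**Scope of the threshold.** The p<0.05 sentence directly follows the taxon sentence and does not say which tests it covers. Its application to the diversity tests is therefore a reading, although no other criterion is given for them. On either reading, how multiplicity is handled for these tests is unspecified.

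**Several metrics.** Reporting several alpha and beta metrics in a pilot is a legitimate choice. The gap is only that none is designated primary and that the rest are neither corrected nor labelled exploratory.

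**Conclusion.** The point holds in a limited form. Aim 4 has a significance rule, six named diversity metrics, no primary one, and a correction stated only for taxa. With no omega-3 effect, the chance of at least one nominally significant diversity result is 26.5% for six independent tests and about 11-19% at assumed correlations of 0.6-0.9. The 24-test figures, 71% if independent and about 21-54% if correlated, apply only if the four sample classes are tested separately. The sizes rest on assumed correlations, on two-sided testing, and on reading the p<0.05 rule as covering the diversity tests. The direction does not depend on the correlation chosen within the range shown. Because this is an estimation pilot with intervals already planned, this should be corrected but does not threaten the trial's main purpose.

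**What to change.** In the Aim 4 text of section 7.1, before any unblinded microbiome data are analysed:

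1. Name one metric, one specimen type, one epithelium and one between-arm change contrast as the Aim 4 primary test, and apply p<0.05 to that test. Use the same definition in section 3.2.
2. Label all other diversity tests exploratory, and extend to them the FDR correction already used for taxa.
3. State whether the four specimen-by-epithelium classes are analysed separately or together, so that the number of tests is known.

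The 95% intervals already planned in section 7.1 can stay as they are. The change is to wording only and needs no new samples, assays, visits or participants. Its downside is that fewer diversity results may be called significant.
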